B2566-P

Effects of rTMS on Brain Activation in Aphasia

NCT03292471

Date: March 6, 2017

A. Background and Significance:

Aphasia is a neurogenic language disorder that is present in approximately one third of acute stroke patients [1], with 60% of cases persisting into the chronic phase (> 6 months post stroke) [2]. Aphasia not only impacts interpersonal communication, but also participation in activities of daily living, independence and autonomy [3]. Furthermore, aphasia severity is positively associated with higher rates of depression and lower health related quality of life (HRQoL), a measure of an individual's perceived physical and mental well-being [4-5]. Lower HRQoL is associated with increased rates of disease-specific morbidity and mortality independent of traditional risk factors [6-9] and critically, *improvements* in HRQoL have been associated with decreased risk [9]. Therefore, decreasing the communicative impairment associated with aphasia has the potential to have broad and significant consequences on Veteran's health.

Encouragingly, a growing number of studies are finding that aphasia therapy is effective well into the chronic phase although treatment response between individuals remains highly variable [10]. It is crucial to understand why some people with chronic aphasia benefit from treatment more than others in order to refine intervention approaches and improve outcomes. One factor that is hypothesized to contribute significantly to the degree of individual language recovery is cortical reorganization, although the most beneficial patterns of reorganization, or how to best induce them, are still under debate. This study proposes to investigate the ability of repetitive transcranial magnetic stimulation (rTMS) to elicit functional cortical reorganization associated with improved language function in study participants with chronic aphasia. The results from this study will both extend existing knowledge regarding the brain-basis of language recovery and inform how rTMS can best be applied to encourage reorganization-related recovery in chronic aphasia.

A1. Effect of hemispheric recruitment on language recovery in aphasia

For the majority of individuals, language is supported by a strongly left- lateralized network of brain regions. When a left hemisphere (LH) stroke injures any of the brain regions involved in this network, other regions are recruited in a compensatory fashion via functional cortical reorganization. There is considerable evidence that compensatory recruitment of undamaged left hemisphere perilesional brain regions results in more optimal recovery of language functions than does recruitment of regions in the right hemisphere (RH) [11-14, and many others]. Furthermore, recruitment of LH perilesional regions, specifically left frontal regions, predicts treatment-related increases in correct naming for individuals with chronic aphasia [15-16].

One account for the poorer outcomes related to RH contralesional recruitment has been framed in terms of interhemispheric inhibition. In its undamaged homeostatic state, the LH language network actively inhibits the RH during language-related tasks via transcallosal projections [17]. This is thought to be an adaptation due to LH specialization, and hence optimization, for language tasks, particularly language production. According to this account, when the LH network is damaged as a result of a stroke, the RH is released from this inhibition, allowing it to be recruited during language production tasks. The now overactive RH in return inhibits the preserved perilesional cortical areas in the LH, preventing them from being recruited [18-19]. As the RH is less specialized for language, this hemispheric shift in activation may result in improved language abilities during recovery, albeit improvements that are relatively suboptimal compared to those that result from more efficacious LH perilesional recruitment [13].

A2. Application of non-invasive brain stimulation to optimize cortical reorganization

Based on the inhibition hypothesis described above, several relatively recent studies have used an approach called repetitive transcranial magnetic stimulation (rTMS) to encourage LH perilesional recruitment for language in people with aphasia following stroke. rTMS is a non-invasive brain stimulation technique in which a focal, time-varying magnetic field is applied to a specific brain area to induce neuronal depolarization. rTMS can be used to selectively target a given brain region with a resolution as focal as 0.5 cm³ [20]. Typically, administering a slow (1 Hz) sequence of magnetic pulses via rTMS temporarily reduces cortical excitability in the targeted brain region [21]. Researchers have therefore used 1 Hz rTMS to inhibit the right hemisphere overactivation postulated by the inhibition hypothesis and thus allow for LH perilesional recruitment [12-24, and others; see 25 for meta-analysis, 19 for review].

The area that is most frequently selected as the target of inhibitory rTMS is Pars Triangularis (PTr) in the inferior right frontal lobe. RH PTr has been characterized as an especially disruptive node in the RH compensatory network that in addition to inhibiting the LH, exhibits less efficient and dysfunctional processing compared to its LH counterpart [26-27]. Consistent with this view, a recent meta-analysis of functional neuroimaging studies in aphasia found that RH PTr was the only right frontal brain area that was not activated under the same conditions as its LH counterpart [28]. Support for this approach has been reported by Naser and colleagues [29] who found that naming abilities immediately improved following one session of inhibitory rTMS to RH PTr, but not when applied to other perisylvian RH areas. Although the improvements resulting

from a single session of inhibitory rTMS are transient, studies in which RH PTR has been targeted across repeated sessions have affected naming improvements that accrue over time and persist after the termination of rTMS administration [30-31]. These longer-lasting changes in the dynamics of the language network are possibly a consequence of mechanism changes in the effectiveness of synapses between cortical neurons, similar to long term depression/potential [32]. Thus, language use even outside of the direct context of the rTMS session serves to reinforce the more functional LH-focused language network and consequently, to discourage recruitment of the maladaptive RH one [28]. This view is further supported by the observation that improvements in language measures continue significantly *beyond* the conclusion of rTMS administration, up to several years [33].

A3. Potential sources of response variability to rTMS

A.3.1 Baseline cortical excitability

Despite the strong positive evidence for the effectiveness of inhibitory rTMS to RH PTR to improve naming in chronic aphasia, not every individual responds significantly [34]. One potential explanation for this finding is that the effect of 1Hz rTMS is state dependent. That is, it has a stronger inhibitory effect when administered to a brain region that has a higher level of excitability [35]. For example, the inhibitory effect of 1 Hz rTMS is *stronger and lasts longer* when participants move their hand prior to rTMS stimulation of the portion of the motor cortex containing the representation of the hand. Perhaps more importantly, inhibitory rTMS has been found to have a paradoxical *excitatory* effect when applied to brain regions already in a state of inhibition [36].

Researchers in the stroke motor-recovery literature have controlled for the potential paradoxical effect of 1 Hz rTMS by first administering a 6 Hz rTMS pulse sequence. In contrast to slow rTMS, pulse sequences above 5 Hz have an excitatory effect [37]. This excitatory pulse sequence in essence “primes” the targeted brain region so that the 1Hz pulse sequence has the expected inhibitory effect, while at the same time enhancing the effect [38]. To date, only one study has applied an excitatory priming sequence to control for potential varying levels of cortical excitability in aphasia. In this study by Kakuda and colleagues [39], participants received 10 minutes of 6 Hz priming stimulation prior to 20 minutes of 1 Hz low-frequency rTMS to RH PTR every weekday for two consecutive weeks. The rTMS was followed by 60 minutes of speech-language therapy (SLT). Improvement was noted for all four participants on both receptive and expressive language measures following the series of rTMS sessions. However, this study had several critical limitations, most notably that all participants received speech-language therapy as part of the protocol. It is therefore impossible to determine the source of the measured improvements (the rTMS, the SLT, or their interaction). In addition, as all participants received the excitatory priming sequence, the study was unable to conclude whether the excitatory priming produced any additional benefit above and beyond that of the standard 1Hz rTMS protocol.

It is highly likely that pre-rTMS RH PTR excitability *would* differ between individuals with chronic aphasia depending on the extent to which it is recruited during recovery. If an individual with chronic aphasia retained some function of LH PTR, which would be expected for those individuals without left frontal lesions, they would not be expected to demonstrate a large amount of compensatory recruitment of RH PTR [28], and hence show little benefit from rTMS induced inhibition of this area. In fact, Kakuda and colleagues in a different study [40] found that the location of peak activation during functional magnetic resonance imaging (fMRI) of a repetition task was in the left hemisphere perilesional areas for over half of the participants with chronic aphasia in their study. *Therefore, it is imperative to have pre-rTMS neuroimaging measures of levels of RH PTR activation in order to accurately interpret the rTMS effects.*

A.3.2 Extent of left-hemisphere focused shift in activation

There is little direct neuroimaging evidence to support the hypothesis that inhibitory rTMS to RH PTR promotes recruitment of intact LH perilesional cortical areas. Several of the rTMS studies in aphasia that measured functional activation did so only *prior* to rTMS and did not investigate pre-post rTMS changes [40-41]. To date there have been only two studies that have investigated differences in task-related regional brain activation *before* and *after* inhibitory rTMS to RH PTR in order to test this hypothesis. Martin and colleagues [34] found that, for one participant, a LH shift in activation post-rTMS corresponded to improved naming, whereas for the other participant, for whom no naming improvement was seen, no such activation shift was noted. Despite offering support for the inhibition hypothesis, this study has several significant limitations. First, the authors used a blocked functional magnetic resonance imaging (fMRI) design to measure naming-related brain activation. Although the block design offers more power to detect small effects, neural responses to individual trials within a block cannot be evaluated separately. This is especially important when evaluating lateralization of activation during naming as other studies have noted differences in lateralization for correct compared to incorrect naming responses in chronic aphasia [26]. Secondly, post-rTMS fMRI scans were only performed beginning at 3 months after rTMS conclusion. Because of this delay, it is unclear whether the

observed activation changes are a cumulative result of the multiple rTMS sessions (via the LTD-like effect), experience-dependent reinforcement of the newly recruited areas within the LH language network, or both. Finally, the study included only 2 participants, limiting the statistical power and analyses that could be performed as well as the generalizability of the findings to a broader group of individuals with chronic aphasia.

A case study published by Turkeltaub and colleagues [27] evaluated the immediate neurobiological effects of inhibitory rTMS. The single participant performed an overt naming task (identical to the one used by Martin et al [30] discussed above) while undergoing an fMRI scan immediately prior to and following the first rTMS session in a series. The rTMS immediately reduced activity at the site of stimulation (RH PTr), but no corresponding LH laterality shift was observed. Furthermore, a subsequent RH stroke further worsened the participant's aphasia symptoms, suggesting that some RH areas exclusive of RH PTr were involved in the initial rTMS induced recovery. However, this evidence is indirect and does not preclude both RH and LH recruitment, nor does it suggest that RH recruitment is *as efficient* as LH recruitment.

Finally, no studies to date have directly tested the claims of the inhibition hypothesis regarding the effect of rTMS on directional inhibitory influences between the RH and LH. To evaluate these claims it is important to measure not only activity changes but also *interactivity* changes to see how the *system* is changing as a result of rTMS across time. Furthermore, as no study has yet collected functional neuroimaging measures throughout the rTMS time course, it is impossible to infer how the acute effects of rTMS relate to the cumulative effects of multiple rTMS sessions, or longer-term changes that occur weeks and months after the conclusion of rTMS.

In summary, inhibitory rTMS targeting RH PTr appears to be a promising approach to treating language difficulties, particularly naming deficits, in chronic aphasia. However, before regular clinical use of rTMS can be considered, we need to have a better understanding of both the *potential sources of response variability*, and the *neurobiological mechanisms* underlying the beneficial effects of rTMS.

B. Preliminary Studies

Several methodological considerations will allow for a more accurate account of the patterns of functional activation for the participants with aphasia. First, an event-related study design will be used in which brain responses to correctly and incorrectly named items can be distinguished and compared across time-points [26]. Secondly, measurements of hemodynamic response (HRF), which are used to estimate the neural response related to the naming event, will be calculated for each individual participant. This is important because individuals with aphasia are known to have delayed HRF or HRF that is decreased in amplitude, resulting in erroneous or underestimated measures of brain activity when canonical HRF estimates are used [43]. Third, dynamic (activity-dependent), directional coupling, known as effective connectivity, will be estimated for regions in the RH and LH to measure interactivity changes across time resulting from rTMS.

C.1 Procedures:

The schedule of study procedures across the 13 study sessions is summarized in Figure 4. During the initial session, enrolled participants will be assessed with the Philadelphia Naming Test (PNT; [44]) and the Comprehensive Aphasia Test (CAT; [45]). In cases where apraxia of speech is suspected, the Apraxia Battery for Adults (ABA-2; [46]) may be administered in whole or in part. Participants may also be assessed with other psycholinguistic and naming measures. The first session will conclude with the baseline MRI scan (described in detail below). If, following the screening session, a participant is found to be eligible they will be scheduled for all remaining study-related visits.

The second visit will begin with the first rTMS session (also described below) which will then be followed directly by the post-rTMS MRI scan. Starting the following day, the subsequent nine sessions will consist only of rTMS for a total of 10 rTMS sessions. The sessions in the rTMS series will take place daily across two weeks excluding weekends. A post-testing session, scheduled the week after the final rTMS session, will include an MRI scan and repeat administration of the language assessments that were administered during the screening visit. A final follow-up session, identical in design to the post-testing session, will be scheduled in an additional 7-10 weeks. All study-related evaluations will be administered by the PI (a licensed speech-language pathologist) or in Year 2 by the staff speech-language pathologist. Study participants will receive up to \$275 for time and local travel expenses and up to an additional \$1500 to defray lodging expenses incurred as part of study participation, to be pro-rated if they do not complete all study procedures (including follow-up visits).

Participants will be pseudo-randomly assigned to an rTMS treatment group (priming stimulation vs no priming stimulation) depending on the outcome of their baseline fMRI (described in C1.1, below). That is, an equal number of participants with and without baseline RH PTr activation will be approximated in each group.

C.1.1 MRI Procedure

fMRI Overt Confrontation Picture Naming Task. Images will be acquired using a 3.0 Tesla parallel-acquisition, echo-planar equipped Siemens MRI scanner. Participants will lay supine in the scanner wearing hearing protection and over-ear headphones. Their heads will be secured with foam padding to minimize movement.

During the fMRI session, picture stimuli will be projected onto a screen placed at the rear of the MRI scanner with E-Prime 2.0 (Psychology Software Tools) software, which subjects will be able to see via a head coil-mounted mirror. Participants will be asked to name the pictures aloud as quickly and accurately as possible. Picture stimuli will consist of black and white line drawings of objects drawn from the Center for Research in Language International Picture Naming Project Database (CRL-IPNP; [47]) and will exclude any items that overlap with the CAT and PNT to avoid repetition effects. The pictures will be presented for 2000 msec with a between-picture ISI between 4-16 seconds, jittered by 2 second intervals. Including longer ISIs will allow the HRF to intermittently return to levels approaching baseline in order to more accurately model individual HRF responses. Between pictures, participants will be asked to fixate on a black crosshair that will be centered on the screen. Naming responses will be recorded via a MR-compatible fiber-optic dual-channel noise cancelling microphone (Optoacoustics Ltd.) to allow for offline scoring of both accuracy and response latency. The fMRI scan will consist of 4 runs (experiment segments) of approximately 40 pictures each; with each run lasting approximately 5 minutes. Picture stimuli will be balanced across runs for average item difficulty [42]. The design of this task is similar to the design used by Postman-Caucheteux and colleagues [26] with participants with aphasia, suggesting that it is feasible with this population.

C 1.2 TMS Procedure

We will use a Magstim Rapid or Rapid2 Magnetic Stimulator (Woburn, MA) with the MagStim Double 70 mm alpha coil, to generate the pulses used to find the motor threshold, and the Magstim Double 70mm air cooled coil to generate the pulses of the rTMS treatment during this study. Before starting each treatment, subjects will be instructed to insert earplugs to lessen any possible adverse effect on hearing.

Motor Threshold and Intensity Determination. To standardize TMS stimulation intensity prior to rTMS, a resting motor evoked threshold (MT) will be established based on a distal upper extremity motor response. The MT will be measured by delivering single stimulations to the motor cortex with gradually increasing intensity no more frequently than every 3 sec, i.e. ~0.3 Hertz. Threshold is defined as the lowest intensity of stimulation producing motor evoked potentials of at least 50 μ V (or a visible movement of the digit) in 5 of 10 trials. Our standard stimulation intensity will be 90% of the MT.

Individual fMRI-based coil targeting. Evidence suggests that the degree of spatial resolution required to target specific cortical sites such as the PTr is achieved more readily when rTMS is used in conjunction with image-guided navigation techniques [48]. This stereotactic targeting also ensures more consistent coil placement across sessions. Following individual determination of stimulation intensity, coil placement individually targeted to the RH PTr will be performed using a frameless stereotactic method as described in Neggers and colleagues [49] and will be implemented in the BrainVoyagerQX software neuro-navigation package. Following coil positioning, participants will receive rTMS treatment according to their group assignment (see below).

TMS Administration.

Group A: Inhibitory only rTMS group: Inhibitory 1Hz rTMS will be applied continuously for 1200 pulses (20 minutes) 5 days per week across 2 weeks (10 sessions total).

Group B: Excitatory primed rTMS group: The inhibitory sequence described above will be preceded for each session by priming stimulation which will consist of intermittent 6-Hz rTMS applied in 5 second trains with 25 second intervals between trains for a total 600 pulses (10 minutes).

C2. Data Analysis

C2.1 Analysis of Behavioral Measures: Naming data (item-level performance on the PNT) will be used for analysis of rTMS treatment effects by group. Accuracy data will be analyzed using multilevel linear or logistic regression in R. Models will include fixed effects of session (baseline, post-treatment, follow-up), and group (Group A, Group B) and random effects of subject and item. Analyses may include additional random-effects structure if needed to improve model fit.

C2.2 fMRI Processing/Data Analysis: All processing will be performed using SPM12 (The Wellcome Trust Centre for NeuroImaging, UCL, UK). The concatenated functional image sequences (runs) will be preprocessed with standard fMRI analysis routines that include slice time acquisition correction, realignment,

registration to structural images, spatial normalization, and spatial smoothing. The data will also be filtered for low frequency scanner drift.

Within-subject data (first level) will be analyzed using a general linear model with a finite impulse response (FIR) basis function to model the individual HRF. For each participant, we will generate an individualized map of brain activity for the contrast of naming > baseline (crosshair fixation) including factor of MRI session for both correct and incorrect responses. Movement parameters will be entered as regressors of no interest to control for participant head movement in the scanner. Activation maps for all contrasts will be thresholded to $p=0.05$ (cluster corrected using Family-Wise Error (FWE)). Resulting contrast values (effect sizes) for each contrast will be entered into a second level/random effect analysis by group (Group A: inhibitory only rTMS vs Group B: excitatory primed inhibitory rTMS). Region of Interest (ROI) analysis will be performed to estimate activation for RH PTr for all described contrasts using the MarsBaR toolbox for SPM.

To assess the relative contribution of the right versus left hemisphere (hemispheric lateralization) to the fMRI naming task, whole brain laterality indices (LI) will be calculated for each scan using the LI-toolbox for SPM [50]. As LI calculation relies on the computation $LI = (Left-Right) / (Left+Right)$, a negative value indicates a right hemispheric dominance and a positive value indicates a left hemispheric dominance. LI values will be generated using t-maps from the first level analyses described above.

Dynamic causal modeling (DCM) will be used to estimate effective connectivity changes due to inhibitory rTMS across time. Regions to be included in the DCM analysis will be derived from clusters of contiguous voxels surviving an omnibus F-test for the effect of interest (correct naming > crosshair fixation) at $p < 0.001$ uncorrected from the first-level fMRI analysis. Regions will be constrained to only include those clusters that fall within the traditionally outlined “language network” in the LH (inferior frontal lobe, temporal lobe, and portions of the inferior and posterior parietal lobe, [51]) and the corresponding RH homologues. The effective connectivity model (estimate of coupling and weights between these regions) will be estimated via post-hoc network discovery methods [52]. This method uses Bayesian model selection methods to select the model that was the most likely to have generated the time series data from all possible combinations of bi-directional connections between the regions. Coupling weights for interhemispheric connections will be summed for each participant for each scanning session. Other post-hoc analyses of the DCM results may be undertaken to explore both inter- and intra-hemispheric network level effects of the rTMS.

Finally, change in naming accuracy on the PNT across sessions will be correlated with change in LI, functional activation in RH PTr, and interhemispheric effective connectivity across sessions. A positive correlation between naming gains and 1) a left-hemisphere directed LI shift, and 2) a decrease in RH inhibition of LH (more positive RH to LH directional coupling weights) will support Hypothesis 1a and 1b, respectively. A positive correlation between the magnitude of pre-TMS RH PTr activation and 1) decrease in RH PTr activation across scan sessions, and 2) magnitude of left-hemisphere directed LI shift will support Hypothesis 2a and 2b, respectively. A significant interaction of group and session (analysis C2.1) suggesting that Group B receiving the 6 Hz primed inhibitory rTMS showed greater naming improvement across time will support Hypothesis 3.

Study timeline: Average estimated participant enrollment length is 10-14 weeks including follow-up, therefore participant recruitment will conclude 4 months prior to last planned data collection. Planned enrollment will be 6 participants in Year 1 and 10 in Year 2. The accelerated enrollment will be made possible in Year 2 due to the proposed hiring of an additional 5/8 staff speech-language pathologist who will assist with participant recruitment, assessment, analyses, and manuscript preparation. Further, as ASPRR has a current enrollment of 133 individuals with aphasia (84 Veterans), and the VAPHS clinical service has historically received approximately 8 new outpatient aphasia treatment referrals per quarter, this enrollment target is feasible.

Task	Protocol Preparation and Refinement				Preliminary Analyses and Conference Submission(s)								Analysis and Manuscript Preparation, Preparation of Subsequent Grants (CDA-2, Merit Award)											
	Participant Recruitment																							
	Participant data collection										Year 2 Staff SLP search													
Month	1	2	3	4	5	6	7	8	9	10	11	12	13	14	15	16	17	18	19	20	21	22	23	24

Table 2: Study timeline

Future Directions: If the proposed study is successful, a subsequent Merit Review application will investigate: 1) use of rTMS to augment treatment gains for well-established behavioral interventions; 2) connection of regions modulated by rTMS to prominent neurocognitive models of naming; and 3) relationships between changes in functional (effective) and structural (white matter) brain connectivity. Addressing these goals will both inform theoretical understanding of aphasia recovery and bring rTMS closer to direct clinical applicability.

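### The method of pseudo-random assignment is not described and balance on the scan result is only approximate, which leaves Hypothesis 3 exposed to predictable assignment; the balancing factor is also missing from the C2.1 model

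*Combined protocol and SAP*

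**What the plan says.** Section C.1 Procedures states that "Participants will be pseudo-randomly assigned to an rTMS treatment group" (priming or no priming) "depending on the outcome of their baseline fMRI". The aim is that "an equal number of participants with and without baseline RH PTr activation will be approximated in each group". The available text gives no method for generating a sequence, no concealment, no named assigner and no cut-off that separates scans with activation from scans without. Some pages between the Preliminary Studies heading and section C.1 were not available, so these items can only be called not described in the text at hand.

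The same section places the naming test (PNT), the aphasia battery (CAT) and the baseline scan in the first session. It has the principal investigator, or in Year 2 the staff speech-language pathologist, administer every evaluation.

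On analysis, C2.1 says: "Models will include fixed effects of session (baseline, post-treatment, follow-up), and group (Group A, Group B"), plus random effects of subject and item. Further random-effects structure is optional. Baseline RH PTr activation is not listed as a term. At the end of C2.2, Hypotheses 1 and 2 are judged by correlations, while Hypothesis 3 is judged by the group by session interaction from C2.1. C2.2 also has fMRI contrast values "entered into a second level/random effect analysis by group", without tying that analysis to a numbered hypothesis. The Study timeline section gives the sample size: "Planned enrollment will be 6 participants in Year 1 and 10 in Year 2".

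**The concern.** Two separate weaknesses bear on Hypothesis 3.

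The first is allocation. A comparison of primed with unprimed stimulation is protected from selection only if nobody who knows the participant can foresee or influence the next assignment. The plan fixes a balance target but does not say how it is reached. If the target were met by inspecting the running tally, staff who already know the naming scores and the scan could anticipate the next group. Without a classification rule, a borderline scan could also be placed in either category. With about 8 per group, a few such decisions would matter.

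The second is the model, and it needs no suspicion of bias. Section A.3.1 argues that people who do not recruit RH PTr strongly should gain little from inhibiting it. The design balances on that factor and the analysis then ignores it. If the factor predicts gain, the between-group standard error includes variation that the design has already removed from the comparison. The test then loses precision and becomes conservative.

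**Working it through.** The plan contains no power or sample-size calculation to reproduce. Everything below except the enrolment figure rests on stated assumptions.

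**Inputs.** Enrolment is 6 + 10 = 16 (Study timeline). Assumed: 1:1 allocation, so 8 per group; two-sided 5% level (the plan states 0.05 only for activation maps); outcome is change in naming in SD units, compared by a two-sample t-test. This simplifies the item-level multilevel model of C2.1.

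**Scale.** The standard error of a group difference is sqrt(2/8) = 0.5 SD. With 14 degrees of freedom, the difference detectable with 80% power is about 1.51 SD.

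**Allocation, one illustrative arrangement.** Suppose two participants, each with 1 SD better expected gain, both enter Group B instead of one entering each group. The shift is 2/8 x 1 = 0.25 SD, or 0.25/0.5 = 0.5 standard errors. With a non-central t (14 df, non-centrality 0.5), the chance of falsely favouring Group B is 0.068, against a nominal 0.025.

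**Allocation, predictability.** Trials of 16 in two strata were simulated with no true effect (8,000 per scenario; stratum prevalence 25% or 50%). The assigner guesses the next group from past assignments in the stratum and steers, so that participants expected in B exceed those expected in A by an assumed 0.5 SD. The row for random block sizes was run with 20,000 trials per prevalence.

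| Scheme | Correct guesses | Bias (SD) | Two-sided error |
|---|---|---|---|
| Alternation within stratum (worst reading of the text) | 94% | about 0.45 | 13-14% |
| Blocks of 2, past assignments known | 73% | 0.23-0.24 | 7% |
| Blocks of 4, past assignments known | 69% | 0.19 | 6-7% |
| Random blocks of 2 and 4, past assignments known | 70% | about 0.20 | about 6% |
| Unpredictable concealed list | 50% | none | 5% |

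Under alternation, steering of 0.25 SD gives about 7% error and 1.0 SD about 37%.

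**Model omission.** If the balancing factor explains a share R2 of the variance in gain, the ratio of adjusted to unadjusted standard error is sqrt((1 - R2) x 14/13):

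- R2 = 0: 1.038, a loss of about 4%
- R2 = 0.1: 0.984, a saving of about 2%
- R2 = 0.2: 0.928, a saving of about 7%
- R2 = 0.3: 0.868, a saving of about 13%

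Adjustment breaks even at R2 = 1/14, about 7%. In simulation with 8 per group, equal balanced strata and no true effect, the unadjusted nominal 5% test rejects about 2.8% of the time at R2 = 0.2 and about 2% at R2 = 0.3.

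**Price of the stratum term.** Moving from 14 to 13 degrees of freedom raises the detectable difference from 1.51 to 1.52 SD. Power at a true difference of 1.0 SD goes from 46.1% to 45.7%.

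**The case against.** The plan does not say that anyone balances by judgement. Pseudo-random assignment with approximate balance is also a fair description of a restricted random list, which itself balances only approximately. A reader might infer that assignments are hand-picked or that the comparison is biased. The documents do not support that, because they name no assigner and no method. This stands: what can be claimed is a risk arising from something not described.

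A reader might also fault the plan for assigning after the scan is read. That does not hold, because any stratified scheme needs the stratum first.

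It would likewise be too strong to call Hypothesis 3 the only comparison of the groups, because C2.2 plans a group-level fMRI analysis. It is the only numbered hypothesis decided by group.

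The allocation figures are hypothetical. The 6.8% describes one arrangement, and simple 8:8 randomisation would also put two given participants both in Group B with probability 8/16 x 7/15 = 23%. It shows how sensitive so small a trial is, not the difference between the plan and the fix. Steering would also have to act on expected gain, and the predictor of gain that the plan stresses is the factor being balanced.

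The precision figures come from a change-score t-test. With only a random intercept for subject, between-person variance in gain would not enter the interaction's standard error in this way. With random slopes, item-level noise would dilute the saving. Section A.3.1 also presents priming as a remedy for dependence on baseline excitability, so the factor may act differently in the two groups, and an additive term may not capture all of it. These points limit the numbers. They do not explain why a factor important enough to balance on is left out of the model.

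**Conclusion.** The concern holds in limited form. As written, the allocation procedure gives no assurance that assignment is unpredictable, and Hypothesis 3 depends on that. The exposure is a risk and has not been shown to occur. If assignment were fully predictable and steering were worth 0.5 SD, both assumed, the two-sided error would be about 13-14% instead of 5%. An unpredictable concealed list would keep it at 5%.

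The model omission is certain from C2.1, but its cost depends on an unknown R2. Under the change-score approximation it ranges from a saving of about 13% in standard error at R2 = 0.3 to a loss of about 4% at zero. Where the factor does predict gain, the unadjusted test is conservative.

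Hypotheses 1 and 2 are judged by correlations and are not decided by the allocation. The change is worth making before enrolment. Confidence is medium, because the method of assignment is unstated and some pages were not available.

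**What to change.** In C.1, replace the assignment sentences with a computer-generated list of permuted blocks of random size (2 and 4) within two strata, baseline RH PTr activation present or absent. Define the strata by a region-of-interest rule written down before enrolment starts. The list should be prepared and held by an existing staff member who takes no part in enrolment or assessment, and each assignment revealed only after eligibility and stratum are recorded. In C2.1, add stratum and stratum by session as fixed effects.

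The cost is a short list-generation script, a few protocol sentences and three extra fixed-effect coefficients (one for stratum, two for its interaction with three sessions). That is about one between-person degree of freedom, and adjustment loses slightly if the factor explains less than about 7% of the variance in gain. A stratum may end uneven by one or two. Some predictability remains if enrolling staff know past assignments (about 70% correct guesses in the simulation), so the list holder should keep block sizes undisclosed and past assignments should be shared as little as practicable.
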